## OBJECTIVES

### 1.1 Study Design

This is a Phase 2 study of pembrolizumab in patients with recurrent or progressive high-grade meningioma.

### 1.2 Primary Objective

To estimate the progression-free survival at 6 months of pembrolizumab in recurrent high-grade meningioma (WHO grade II atypical meningioma and WHO grade III anaplastic meningioma)

### 1.3 Secondary Objectives

1. To determine the toxicity of pembrolizumab in patients with recurrent high-grade meningioma (WHO grade II atypical meningioma and WHO grade III anaplastic meningioma)
2. To estimate the overall survival of patients with recurrent high-grade meningioma receiving pembrolizumab
3. To estimate the response rate of patients with recurrent high grade meningioma receiving pembrolizumab

### 1.4 Exploratory Objectives

1. To determine molecular biomarkers of response using RNAscope in situ hybridization methodologies for immune checkpoint markers, immunohistochemistry to characterize the immune infiltrate and next generation DNA and RNA sequencing.
2. To determine if changes in brain MRI parameters correlate with tumor response.

## 2. BACKGROUND

### 2.1 Meningioma

Meningiomas are the most common primary brain tumor, with a prevalence of 170,000 cases in the US and an annual incidence of 18,000 new cases. Most meningiomas are of the typical variety – World Health Organization (WHO) grade I. However, depending on their location within the nervous system, grade I meningiomas can cause significant morbidity or mortality. Even after surgical resection, recurrence rates can be as high as 20%, and patients with grade I tumors have reduced long-term survival.

Approximately 20% of meningiomas are atypical (WHO grade II) and anaplastic (WHO grade III), defined by increased mitoses, necrosis, higher nuclear to cytoplasmic ratios, or histologic appearance resembling carcinoma, sarcoma, or melanoma. Recurrence rates for WHO grade II and III meningiomas are 40% and 80%, respectively. The prognosis of atypical and anaplastic meningiomas is poor, with 5-year overall survival rates between 47-65%.

Treatment options, particularly for the atypical or anaplastic meningiomas, are limited. Radiation is frequently used as an adjunct to surgery; however, there are no effective chemotherapeutic options when surgery and radiation fail to offer durable long-term disease

control. Traditional cytotoxic agents have minimal activity in this setting, and targeted agents in unselected patients have demonstrated modest benefit at best. Response rate has been 0% in nearly all studies of systemic therapy in recurrent tumors of all grades. A poor understanding of what drives meningioma development has hampered the development of therapeutic agents to supplement surgery and radiation. Therefore these patients have limited therapeutic options and effective treatments are greatly needed. While genomic studies have revealed mutations in oncogenes such as SMO and AKT in a small subset of meningioma, most tumors do not have mutations that can be targeted. Studies of high grade tumors have failed to reveal obvious drivers of malignant progression, rendering these tumors exceedingly challenging to treat.

## **2.2 Pembrolizumab (MK-3475)**

The importance of intact immune surveillance in controlling outgrowth of neoplastic transformation has been known for decades. Accumulating evidence shows a correlation between tumor-infiltrating lymphocytes (TILs) in cancer tissue and favorable prognosis in various malignancies. In particular, the presence of CD8+ T-cells and the ratio of CD8+ effector T-cells / FoxP3+ regulatory T-cells seems to correlate with improved prognosis and long-term survival in many solid tumors.

The PD-1 receptor-ligand interaction is a major pathway hijacked by tumors to suppress immune control. The normal function of PD-1, expressed on the cell surface of activated T-cells under healthy conditions, is to down-modulate unwanted or excessive immune responses, including autoimmune reactions. PD-1 (encoded by the gene *Pdcd1*) is an Ig superfamily member related to CD28 and CTLA-4 which has been shown to negatively regulate antigen receptor signaling upon engagement of its ligands (PD-L1 and/or PD-L2). The structure of murine PD-1 has been resolved. PD-1 and family members are type I transmembrane glycoproteins containing an Ig Variable-type (V-type) domain responsible for ligand binding and a cytoplasmic tail which is responsible for the binding of signaling molecules. The cytoplasmic tail of PD-1 contains 2 tyrosine-based signaling motifs, an immunoreceptor tyrosine-based inhibition motif (ITIM) and an immunoreceptor tyrosine-based switch motif (ITSM). Following T-cell stimulation, PD-1 recruits the tyrosine phosphatases SHP-1 and SHP-2 to the ITSM motif within its cytoplasmic tail, leading to the dephosphorylation of effector molecules such as CD3 $\zeta$ , PKC $\theta$  and ZAP70 which are involved in the CD3 T-cell signaling cascade.

The mechanism by which PD-1 down modulates T-cell responses is similar to, but distinct from that of CTLA-4 as both molecules regulate an overlapping set of signaling proteins. PD-1 was shown to be expressed on activated lymphocytes including peripheral CD4+ and CD8+ T-cells, B-cells, T regs and Natural Killer cells. Expression has also been shown during thymic development on CD4-CD8- (double negative) T-cells as well as subsets of macrophages and dendritic cells. The ligands for PD-1 (PD-L1 and PD-L2) are constitutively expressed or can be induced in a variety of cell types, including non-hematopoietic tissues as well as in various tumors. Both ligands are type I transmembrane receptors containing both IgV- and IgC-like domains in the extracellular region and contain short cytoplasmic regions with no known signaling motifs. Binding of either PD-1 ligand to PD-1 inhibits T-cell activation triggered through the T-cell receptor.

PD-L1 is expressed at low levels on various non-hematopoietic tissues, most notably on vascular endothelium, whereas PD-L2 protein is only detectably expressed on antigen-presenting cells found in lymphoid tissue or chronic inflammatory environments. PD-L2 is thought to control immune T-cell activation in lymphoid organs, whereas PD-L1 serves to dampen unwarranted T-cell function in peripheral tissues. Although healthy organs express little (if any) PD-L1, a variety of cancers were demonstrated to express abundant levels of this T-cell inhibitor. PD-1 has been suggested to regulate tumor-specific T-cell expansion in subjects with melanoma (MEL). This suggests that the PD-1/PD-L1 pathway plays a critical role in tumor immune evasion and should be considered as an attractive target for therapeutic intervention.

Pembrolizumab is a potent and highly selective humanized monoclonal antibody (mAb) of the IgG4/kappa isotype designed to directly block the interaction between PD-1 and its ligands, PD-L1 and PD-L2. Keytruda™ (pembrolizumab) has recently been approved in the United States for the treatment of patients with unresectable or metastatic melanoma and disease progression following ipilimumab and, if BRAF V600 mutation positive, a BRAF inhibitor.

An open-label Phase I trial (Protocol 001) is being conducted to evaluate the safety and clinical activity of single agent MK-3475. The dose escalation portion of this trial evaluated three dose levels, 1 mg/kg, 3 mg/kg, and 10 mg/kg, administered every 2 weeks (Q2W) in subjects with advanced solid tumors. All three dose levels were well tolerated and no dose-limiting toxicities were observed. This first in human study of MK-3475 showed evidence of target engagement and objective evidence of tumor size reduction at all dose levels (1 mg/kg, 3 mg/kg and 10 mg/kg Q2W). No MTD has been identified to date. 200mg IV Q3W will be the dose and schedule utilized in this protocol to test for initial tumor activity. Recent data from other clinical studies within the MK-3475 program has shown that a lower dose of MK-3475 and a less frequent schedule may be sufficient for target engagement and clinical activity.

Analysis of pharmacokinetic data for MK-3475 administered Q2W and Q3W showed slow systemic clearance, limited volume of distribution, and a long half-life. Pharmacodynamic data (IL-2 release assay) suggested that peripheral target engagement is durable (>21 days). This PK and pharmacodynamic data provides scientific rationale for using a Q3W dosing schedule.

A population pharmacokinetic analysis has been performed using serum concentration time data from 476 patients. Within the resulting population PK model, clearance and volume parameters of MK-3475 were found to be dependent on body weight. The relationship between clearance and body weight, with an allometric exponent of 0.59, is within the range observed for other antibodies and would support both body weight normalized dosing or a fixed dose across all body weights. MK-3475 has been found to have a wide therapeutic range based on the melanoma indication. The differences in exposure for a 200 mg fixed dose regimen relative to a 2 mg/kg Q3W body weight based regimen are anticipated to remain well within the established exposure margins of 0.5 – 5.0 for MK-3475 in the melanoma indication. The exposure margins are based on the notion of similar efficacy and safety in melanoma at 10 mg/kg Q3W vs. the proposed dose regimen of 2 mg/kg Q3W (i.e. 5-fold higher dose and exposure). The population PK evaluation revealed that there was no significant impact of tumor burden on exposure. In addition, exposure was similar between the NSCLC and melanoma indications. Therefore, there are no anticipated changes in exposure between different indication settings.

The rationale for further exploration of 2 mg/kg and comparable doses of pembrolizumab in solid tumors is based on: 1) similar efficacy and safety of pembrolizumab when dosed at either 2 mg/kg or 10 mg/kg Q3W in melanoma patients, 2) the flat exposure-response relationships of pembrolizumab for both efficacy and safety in the dose ranges of 2 mg/kg Q3W to 10 mg/kg Q3W, 3) the lack of effect of tumor burden or indication on distribution behavior of pembrolizumab (as assessed by the population PK model) and 4) the assumption that the dynamics of pembrolizumab target engagement will not vary meaningfully with tumor type.

The choice of the 200 mg Q3W as an appropriate dose for the switch to fixed dosing is based on simulations performed using the population PK model of pembrolizumab showing that the fixed dose of 200 mg every 3 weeks will provide exposures that 1) are optimally consistent with those obtained with the 2 mg/kg dose every 3 weeks, 2) will maintain individual patient exposures in the exposure range established in melanoma as associated with maximal efficacy response and 3) will maintain individual patients exposure in the exposure range established in melanoma that are well tolerated and safe.

A fixed dose regimen will simplify the dosing regimen to be more convenient for physicians and to reduce potential for dosing errors. A fixed dosing scheme will also reduce complexity in the logistical chain at treatment facilities and reduce wastage.

### **2.3 Rationale**

Recently, great strides in immunotherapies have been made in the management of a number of malignancies namely the development of the immune checkpoint inhibitors targeting cytotoxic T-lymphocyte antigen 4 (CTLA4) and the programmed cell death (PD1) receptor-ligand (PDL1, PDL1). However, the role of these inhibitors in meningioma has not been explored. Preclinical data demonstrates an increase in PD-L1 expression as meningioma tumor grade increases and a decrease in the number of T-cells in higher grade meningioma. Because there are no effective medical treatments for recurrent WHO grade II atypical and WHO grade III anaplastic meningioma we characterized the immune infiltrate of meningioma and investigated the expression of molecules that might render these tumors susceptible to checkpoint blockade. We characterized the immune infiltrate of 291 meningiomas including WHO grade I-III meningiomas using immunohistochemistry and we examined the expression of PD-L1 mRNA by RNAscope in situ hybridization and PD-L1 protein by immunohistochemistry and flow cytometry. In meningioma, the tumor infiltrating lymphocytes are predominantly T cells. In atypical and anaplastic meningioma, there is a sharp decrease in the number of T cells, including the numbers of CD4+ and CD8+ T cells and there is also an increase in the number of FOXP3 expressing immunoregulatory (Treg) cells. PD-L1 mRNA and protein expression is increased in atypical and anaplastic meningioma. Using patient derived meningioma cells, we confirmed that PD-L1 is expressed in meningioma cells themselves, and not solely in infiltrating immune cells. This work indicates that high-grade meningioma harbor an immunosuppressive tumor microenvironment and that increased Treg cells and elevated PD-L1 may contribute to the aggressive phenotype of these tumors.

We now hypothesize that patients with meningioma expressing PD-L1 will respond to

checkpoint blockade with pembrolizumab. We are thus proposing a prospective Phase 2 study of the PD-1 inhibitor pembrolizumab in patients with recurrent high grade (WHO grade II and III) using a dose schedule that has demonstrated efficacy in systemic tumors. We propose to investigate the activity of pembrolizumab in a single cohort. We propose to incorporate monitoring with MR imaging, and pathology correlates from tissue resections (IHC markers for characterizing the immune infiltrate including PD-1 expressing cells and PD-L1 expression of the tumors via IHC and mRNA in situ hybridization/quantitative RNAscope), and next generation DNA sequencing and RNA-sequencing to identify genetic and imaging predictors of response.

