**3.1.3 Prior Treatment**

- Prior medical therapy is allowed but not required.
- Meningioma that have resulted from prior radiation therapy are allowed.
- No limit on number of prior therapies.
- No chemotherapy, other investigational agents within 14 days of study treatment.
- No other concurrent investigational agents or other meningioma-directed therapy (chemotherapy, radiation) while on study.
- For patients treated with external beam radiation, interstitial brachytherapy or radiosurgery, an interval  $\geq 24$  weeks must have elapsed from completion of XRT to registration.
- Stable dose of dexamethasone 2mg or less for at least 7 days prior to initiation of treatment.
- Recovered to CTCAE grade 1 or less toxicity from other agents with exception of alopecia and fatigue.
- No craniotomy within 21 days of registration.
- Grade I meningiomas will be allowed as long as they meet criteria for progression as defined by 3.1.1.

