### **13.8 Analysis of Exploratory Endpoints**

Biomarkers of blood and tissue: Analyses of blood, imaging, and tissue biomarkers will be based on descriptive statistics, as appropriate for the biomarker.

To examine response according to pre-treatment levels of biomarkers, the study sample will be divided retrospectively according to the primary endpoint of response or non-response. Pre-treatment biomarker levels will be summarized descriptively for the two response groups and compared using Wilcoxon rank-sum tests for markers measured on a continuous scale, or Fisher's exact tests for those measured on a categorical scale. Where appropriate, visualization of the relationship between baseline marker levels and the distributions of PFS or OS will employ Kaplan-Meier estimates stratified by biomarker levels. Medians of the time-to-event endpoints will be shown with two-sided 90% confidence intervals; the distributions of PFS and OS will be compared across biomarker strata using the log-rank test.

Changes in biomarkers between pretreatment and progression or treatment discontinuation will be calculated (post-pre) for each patient and summarized descriptively. In addition, the correlation of changes in tissue biomarkers with changes in measures of peripheral blood markers will be explored graphically, or by appropriate statistical methods based on data availability, to assess associations.

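### The exploratory biomarker tests in 13.8 ignore WHO grade, which the protocol ties to both the markers and recurrence; if grade is prognostic here, PD-L1 results are biased against the hypothesis and T-cell results in favor.

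*Combined protocol and SAP*

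**What the plan says.** **Markers and grade (2.3).** "Preclinical data demonstrates an increase in PD-L1 expression as meningioma tumor grade increases". In atypical and anaplastic tumors, "there is a sharp decrease in the number of T cells, including the numbers of CD4+ and CD8+ T cells". The section concludes that "increased Treg cells and elevated PD-L1 may contribute to the aggressive phenotype of these tumors".

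**Hypothesis (2.3).** "We now hypothesize that patients with meningioma expressing PD-L1 will respond to" pembrolizumab. Biomarkers of response are the first exploratory objective (1.4).

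**Grade and outcome (2.1).** "Recurrence rates for WHO grade II and III meningiomas are 40% and 80%, respectively".

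**Who is enrolled.** The objective names grades II and III (1.2). Section 3.1.3 adds: "Grade I meningiomas will be allowed as long as they meet criteria for progression". All patients form one cohort (2.3).

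**Analysis (13.8).** Pre-treatment marker levels in the two response groups are "compared using Wilcoxon rank-sum tests for markers measured on a continuous scale", with Fisher's exact test for categorical markers. For time to event, "the distributions of PFS and OS will be compared across biomarker strata using the log-rank test". Grade is not mentioned. Section 13.4 lists no stratification factors. The only covariate named in the correlative plan is the patient cohort, in the MRI section (9.3.5.3), and a single-cohort trial has nothing to adjust for there.

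**The concern.** A variable linked to both a marker and the outcome distorts the crude association between them. By the protocol's own account grade is linked to PD-L1 and T cells, and very likely to outcome. In a pooled sample, high PD-L1 will partly mean higher grade.

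The bias differs by marker. PD-L1 rises with grade, so a poor prognosis in high-grade tumors works against the hypothesized benefit. T cells fall with grade, so the same mechanism makes abundant T cells look favorable even if they have no effect.

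At stake is the reading of the first exploratory objective. An unadjusted result cannot be separated from grade, and results of this kind are used to choose markers for later trials.

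**Working it through.** **1. The plan's own figure.** The documents state no power for the biomarker tests. The one stated power, in 13.6, is for the primary rule of at least 10 of 24. Exact binomial: P(X ≥ 10 | 24, 0.26) = 0.069 and P(X ≥ 10 | 24, 0.52) = 0.888. The stated 88% power and one-sided 0.1 level reproduce, and this point does not touch them.

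**2. Inputs.** From the documents: 24 evaluable patients (13.3), the direction of the marker-grade links (2.3), and recurrence of 40% and 80% (2.1). The recurrence rates convert to:
- odds ratio (0.80/0.20)/(0.40/0.60) = 6;
- hazard ratio ln(0.20)/ln(0.60) = 3.15, if hazards are constant and follow-up equal.

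These describe recurrence in general, not 6-month PFS on systemic therapy, so they serve as the strong end of a range. Grade mix, marker shift, cut-point and two-sided 0.05 are all assumed.

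**3. Direction, by hand.** Assume 20% grade III and 80% grade II; PD-L1 high in 80% of grade III and 20% of grade II; 6-month PFS in PD-L1-low patients of 50% (grade II) and 20% (grade III); true within-grade odds ratio 2.
- PD-L1-high group: 0.8 × 0.2 = 0.16 grade II and 0.2 × 0.8 = 0.16 grade III, half each. Doubling the odds gives PFS of 66.7% and 33.3%, average 50.0%, odds 1.00.
- PD-L1-low group: 0.64 grade II and 0.04 grade III. PFS = (0.64 × 0.50 + 0.04 × 0.20)/0.68 = 48.2%, odds 0.93.
- Apparent odds ratio: 1.00/0.93 = 1.07, against a true 2.

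Changing only the PFS of PD-L1-low patients:

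| Grade II / grade III PFS | Apparent odds ratio (true 2) | Apparent odds ratio (true 1) |
|---|---|---|
| 50% / 50% | 2.00 | 1.00 |
| 50% / 35% | 1.51 | 0.77 |
| 50% / 20% | 1.07 | 0.58 |
| 55% / 15% | 0.85 | 0.48 |

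Over 36 scenarios (grade III share 20-50%; PD-L1 high in 20-30% of grade II and 50-80% of grade III; PFS 50-55% and 15-50%), a true odds ratio of 2 appears as 0.61 to 2.0. It falls below 1 in 7 of the 36, all with a strong grade effect and a strong PD-L1-grade link.

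**4. Log-rank test at the trial's size (simulation).** n = 24; 40% grade III; marker = standard normal + 1 SD if grade III; exponential PFS with hazard multiplied by the grade hazard ratio and by the marker hazard ratio per SD; no censoring; median split.

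| Grade hazard ratio | False rejection: unadjusted / stratified | Power, true 0.60 per SD: unadjusted / stratified |
|---|---|---|
| 3.15 | about 14% / 6-7% | about 16% / 31% |
| 1.5 | 7-8% / 6% | 35% / 31% |
| 1.0 | not biased | 46% / 32% |

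At 3.15, nearly all the false rejections point to harm from high PD-L1. A significant reversal of a true benefit occurs in about 0.1% of trials.

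**5. Response-group test (simulation).** Outcome taken as 6-month PFS status; n = 24; one third grade III; mean PFS6 45%; Wilcoxon against its grade-stratified (van Elteren) form; true PD-L1 odds ratio 2 per SD.
- Grade odds ratio 6, shift 1.0 SD: power 11% unstratified and 26% stratified; wrong direction in 20% of unstratified trials; significant reversal in 0.2%.
- Grade odds ratio 2, shift 0.5 SD: power 25% and 28%; wrong direction in 9%.
- No grade effect, shift 0.5 SD: power 31% and 28%.
- T cells with no true effect, 1.0 SD lower in grade III, grade odds ratio 6: significantly favorable in 10.6% of unstratified trials (nominal 2.5%) and 2.0% stratified.

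**The case against.** **The grade effect is borrowed.** The 40% and 80% are general recurrence rates without a time horizon. Patients here already have recurrent, progressive or residual disease, which may narrow the grade difference, and the 26% benchmark in 13.6 pools grades II and III. This stands: a hazard ratio of 3.15 is an assumption, and at 1.5 the inflation nearly disappears.

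**Stratifying has a price.** It discards the between-grade part of the marker contrast. If grade is not prognostic, power falls by 14 points (46% to 32%). This stands, and is why adjusted results should accompany the planned ones and not replace them.

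**Grade may lie on the causal path.** Section 2.3 suggests that PD-L1 may contribute to aggressive behavior, in which case adjusting for grade could remove part of its effect. This is arguable, and another reason to show both estimates.

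**The strata matter.** Apart from one general sentence, 2.3 sets grades II and III together against lower grade. Pooling I with II would leave that contrast uncontrolled. With an assumed 25/50/25% mix, shifts of 1-1.5 SD and hazard ratios of 2-3.15 located at I versus II/III, a test stratified as I/II versus III still falsely rejects in 8-14%, against 8-18% unadjusted. This stands and shapes the fix.

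**The work is exploratory.** Section 13.8 is largely descriptive and sets no alpha, cut-point or decision rule. This limits the weight of the point but does not remove it, since the section does name formal tests.

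**Conclusion.** The gap is real: the protocol supplies a likely confounder and no planned biomarker test accounts for it. If grade is prognostic in this trial, the unadjusted PD-L1 association is biased against the hypothesis and the T-cell association toward a spurious favorable finding. On the assumed inputs, PD-L1 false rejection is about 14% against 6-7% stratified at a grade hazard ratio of 3.15, and 7-8% against 6% at 1.5.

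A reader might infer that grade will certainly hide or reverse a true PD-L1 effect, or that the biomarker results would mostly restate grade. The documents do not support that. They give no 6-month PFS by grade, no grade mix and no size for the marker-grade link. Attenuation is the usual result, an apparent reversal needs strong assumptions, and a significant one is rare at this sample size. A reader might also extend the point to the MRI models in 9.3.5.3, but nothing in the documents ties MRI parameters to grade.

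Nor does adjustment make the tests conclusive: in the log-rank simulations stratified power stays near 30%. This is a modest improvement to an exploratory analysis, and the primary endpoint is untouched.

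**What to change.** In 13.8:
- keep the planned tests, and report beside each a grade-stratified or grade-adjusted estimate with its confidence interval: stratified log-rank or Cox for PFS and OS, van Elteren for continuous markers, exact Cochran-Mantel-Haenszel for categorical ones;
- tabulate PD-L1 and T-cell markers by WHO grade;
- keep grade I patients as their own stratum, or exclude them in a sensitivity analysis, and do not pool them with grade II;
- state that a marker will be interpreted as predictive only if its association persists within grade.

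No grade stratum is needed for the MRI models.

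The cost is a few lines of text. Eligibility refers to grade (3.1.1, 3.1.3), so it should be on record, but the baseline list in 5.2 does not name it; confirm that the case report form captures it. The statistical downside is lower power for the adjusted results if grade proves weakly prognostic or a stratum is small.
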